11.2.3 Secondary Endpoint Analyses

11.2.3.1 PSA Response to VTP-850

The number, proportion, and 90% confidence interval (CI) of participants with a PSA response, defined as $\geq 50\%$ reduction in serum PSA compared to baseline and measured twice consecutively, will be summarised by timepoint and overall. This will be further broken down by whether the participants had prior radical prostatectomy or prior external beam radiation. The maximum PSA reduction from baseline will be summarised, as well as by whether participants had prior radical prostatectomy, external beam radiation or brachytherapy.

11.2.3.2 Durable PSA Response to VTP-850 at Month 8

The number, proportion and 90% CI of participants with a durable PSA response at Month 8 will be summarised, among all participants and among those with a response by Month 6. Durable PSA response is defined as having follow-up through Month 8 and a confirmed PSA response without having PSA progression (i.e., an increase relative to nadir of $\geq 25\%$ and an absolute increase of 0.2 ng/mL or more) on or before Month 8. This will be further summarised by whether the participants had prior radical prostatectomy, external beam radiation or brachytherapy.

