4.4. Efficacy Evaluable Set

The Efficacy Evaluable Set (EES) will consist of all participants in the FAS who had one baseline measurement of PSA and at least one post-baseline measurement of PSA. EES participants are analysed according to the dose regimen the participant was allocated.

The EES will be used for analyses of secondary efficacy endpoints which examine PSA response.

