Table 8: Calculation of PSA Response Example

Participant	Timepoint	Study Day	PSA Value (ng/mL)	PSA change from baseline	PSA absolute change from nadir	PSA percent change from nadir
1	Baseline	1	1.6			
1	Day 29	29	1.3	-18.75%		
1	Day 57	57	1.05	-34.38%		
1	Day 64	64	0.90	-43.75%		
1	Month 4	122	0.80	-50.00%		
1	Month 5	152	0.80	-50.00%		
1	Month 6	164	0.81	-49.38%	0.01	1.25%
1	Month 7	226	0.82	-48.75%	0.02	2.50%
1	Month 8	256	0.85	-46.88%	0.05	6.25%
1	Month 9	282	0.75	-53.13%	-0.05	-6.25%

- Responder = Yes
- First observed PSA response = Month 4
- PSA progression = No PSA progression
- Response at Month 8 = Yes (A confirmed PSA response has occurred and no PSA progression)

6.6.2.2. Durable PSA Response to VTP-850 at Month 8

If more than three participants have a confirmed PSA response at month 6 then the number, proportion and 90% CIs of participants with a durable PSA response (having a confirmed PSA response without PSA progression or on or before Month 8) will be presented for each treatment group using the EES. Participants with missing PSA data at Month 8 will have a durable PSA response imputed as described previously in Section 5.2.1. Otherwise, if participants are missing PSA data at Month 8 they will be treated as non-responders. The same summary will also be presented among participants who have a durable response at Month 6.

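### SAP 6.6.2.2 bases its second Month 8 durability summary on an undefined Month 6 group instead of the protocol's responders by Month 6

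*SAP*

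**What the plan says.** Protocol 11.2.3.2 has the Month 8 durable response summarised "among all participants and among those with a response by Month 6". It defines the outcome as follows: "Durable PSA response is defined as having follow-up through Month 8 and a confirmed PSA response without having PSA progression", with progression judged up to and including Month 8.

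SAP 6.6.2.2 gives the summary by treatment group on the Efficacy Evaluable Set (EES), subject to a minimum count: "If more than three participants have a confirmed PSA response at month 6 then" the analysis is presented. It describes a durable response as "having a confirmed PSA response without PSA progression or on or before Month 8". The phrase is garbled, but it plainly corresponds to the protocol's endpoint. The paragraph then adds the conditional summary: "The same summary will also be presented among participants who have a durable response at Month 6".

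The SAP gives no Month 6 version of durable response. SAP section 7 lists one departure from the protocol, the added ECG endpoint, and does not mention this denominator.

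**The concern.** The protocol's conditional summary asks what share of men who responded by Month 6 still hold that response, without progression, at Month 8. A man who responds and then progresses before Month 6 is a failure for that question and belongs in the denominator. A group described as durable at Month 6 appears to leave him out. The figure would then be the chance of lasting about two more months among men who had not yet progressed, which is a different and more favourable quantity.

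This matters more than a supplementary row usually would. SAP 2.2.2 defers duration of PSA response to Phase 2, and SAP 6.6.3 plans no sensitivity analysis. The row is therefore the only planned durability proportion among responders in the Phase 1 report. Protocol 11.1 says that estimated response rates and durability may inform the size and power of later trials.

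**Working it through.** The documents state no durability rate, so there is no figure to reproduce. The check compares the two denominators.

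**Inputs**
- Protocol denominator: confirmed responders by Month 6 (Protocol 11.2.3.2).
- SAP denominator: durable responders at Month 6 (SAP 6.6.2.2), undefined.
- Progression: a rise from nadir of at least 25% "and an absolute increase of 0.2 ng/mL or more) on or before Month 8" (Protocol 11.2.3.2).
- Interval: 90% Jeffreys (SAP 6.6.2.1), that is, the 5th and 95th percentiles of Beta(x+0.5, n−x+0.5), with the upper limit set to 100% when x = n.
- Counts: not in the documents, so assumed. SAP 2.3 expects about 25 men in Phase 1. At the 20% response rate used in Protocol 11.4 that is 25 × 0.20 = 5 responders. The summary needs at least 4, reading the SAP's minimum as confirmed responders to date.

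**Reading (a): durable at Month 6 means a confirmed response without progression by Month 6.** Let R be the confirmed responders by Month 6, k those of them who progress by Month 6, and D those durable at Month 8. Progression by Month 6 is also progression by Month 8, so none of the k men can be in D. Hence:
- Protocol rate = D/R
- SAP rate = D/(R−k)
- Ratio = R/(R−k), which is never below 1 and equals 1 only when k = 0.

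**Reading (b): the only stated definition, no progression by Month 8, is applied.** The denominator is then the numerator, and the rate is D/D = 100% whatever the data.

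**Can k exceed zero on this visit schedule?** Yes. In a constructed case, baseline PSA is 2.0 ng/mL, then 0.8 at Days 29, 57 and 64, 0.9 at Day 91 and 1.1 at Day 120. The fall to 0.8 is 60%, and Days 29 and 57 are 28 days apart, so the response is confirmed. At Day 91 the rise from nadir is 0.1 ng/mL (12.5%), which is not progression. At Day 120 it is 0.3 ng/mL (0.3/0.8 = 37.5%), which is. This man is in the protocol's denominator and, under (a), not in the SAP's.

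**Size under reading (a), assumed counts**

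| R | k | D | Protocol D/R (90% CI) | SAP D/(R−k) (90% CI) | Ratio |
|---|---|---|---|---|---|
| 4 | 0 | 3 | 75.0% (34.9–95.4) | 75.0% (34.9–95.4) | 1.00 |
| 4 | 1 | 2 | 50.0% (16.5–83.5) | 66.7% (23.6–93.8) | 1.33 |
| 4 | 1 | 3 | 75.0% (34.9–95.4) | 100% (55.6–100) | 1.33 |
| 4 | 2 | 2 | 50.0% (16.5–83.5) | 100% (43.1–100) | 2.00 |
| 6 | 2 | 3 | 50.0% (20.9–79.1) | 75.0% (34.9–95.4) | 1.50 |

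These counts are pooled. The SAP presents the summary by treatment group, so each cell would be smaller still.

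**The case against.** The strongest reply is that this is a drafting slip in a minor row. The term has no Month 6 definition, its parent definition is garbled, and the same paragraph speaks of a confirmed response at Month 6 when it sets the minimum count. The author may simply have meant confirmed response. That is plausible, and the documents do not show that the sponsor chose a denominator to raise the rate. But neither literal reading yields the protocol's quantity in general, and a programmer following the text needs the correction either way.

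A reader might also infer that the durability endpoint as a whole is inflated. The documents do not support that. The main summary uses the EES (SAP 4.4: "The EES will be used for analyses of secondary efficacy endpoints which examine PSA response"), where a man who has progressed by Month 6 counts as not durable. Nor does the point extend to Phase 2, which SAP 2.1 leaves to a separate plan.

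Three further points stand and limit the weight of the issue:
- The protocol's ratio can largely be rebuilt from planned tables, since SAP 6.6.2.1 reports confirmed responders and SAP 6.6.2.2 reports durable ones. A reader would still take the labelled row at face value.
- No stated decision rests on it. The Phase 2 regimen is selected on safety data (Protocol 4.1.1), and Stage 2 opens on PSA responses (Protocol 4.1.2).
- With so few responders, the intervals under the two denominators overlap heavily. Imprecision does not make the wrong denominator right.

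**Conclusion.** Wrong as written, with limited reach. The supplementary Month 8 summary departs from Protocol 11.2.3.2 through an undefined term, and SAP section 7 does not declare it. Under the parallel reading the conditional rate is multiplied by R/(R−k): 50% becomes 67% in the illustration with 4 responders, 1 early progressor and 2 durable. Under the literal Month 8 definition it is 100% regardless of the data.

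The direction under the parallel reading is certain, but a difference is not. If no responder progresses by Month 6, the two rates are equal. Early progression is plausible. Protocol 4.1.7 provides for responders who progress more than 2 months after the final dose, which after a Day 57 dose means from about Day 117, well before Day 180. Protocol 2.1 reports that 3 of 5 PSA responses to the predecessor product were transient. That was in a different disease stage and with nivolumab, so it supports plausibility and not a rate.

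The exact ratio assumes that the missing-data rule in SAP 5.2.1, which does not check for progression, never imputes an early progressor as durable. All counts are assumed. The summary is descriptive, so no error rate or power is affected.

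**What to change.** Reword the last sentence of SAP 6.6.2.2 so that the second summary's denominator is every participant with a confirmed PSA response by Month 6, whether or not he has progressed by Month 6. This restores the protocol's group. If a group still free of progression at Month 6 is truly wanted, define it, justify it, list it in SAP section 7, and show it alongside the protocol's summary.

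The cost is one sentence. No new data are needed: SAP 5.2.1 already treats a missing Month 8 PSA as non-response unless its bracketing rule applies, so early progressors who leave follow-up can be counted as failures. The downside for the sponsor is that the reported conditional proportion may be less favourable.

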6.6.3. Sensitivity Analyses for the Secondary Efficacy Analysis

Not Applicable.

6.6.4. Exploratory Analysis

6.6.4.1. Immunogenicity Response to VTP-850

These analyses will be presented using the Immunogenicity analysis set both overall and separately by whether participants had or did not have an observed PSA response.

Background-subtracted overall percentage cytokine expression will be presented for each T cell (CD4+ and CD8+) and stimulation antigen (PSA, PAP, 5T4, STEAP1). Descriptive statistics including n, mean, standard deviation, median, minimum, maximum, and 95% CI for the median based on order statistics will be presented for absolute values, change from baseline, and fold change from baseline at all planned time points (Days 1, 29, 36, 57, 64, 91 and Months 8 and 12). Fold change for values i and j is defined as:

$(\text{Value } j / \text{Value } i) - 1$.

Where value j is the cytokine expression value at a non-baseline timepoint and value i is the cytokine expression value at day 1. When value i is 0 a small constant, λ , will be added to the calculation. $\lambda = 0.5 \times \min$ (non-zero value for all participants at all time points). In this case fold change will be calculated as:

$((\text{Value } j + \lambda) / (\text{Value } i + \lambda)) - 1$.

DMSO (i.e. background) percentage cytokine expression will be presented similarly to background-subtracted overall cytokine response.

Graphical summaries using dot plots for the background-subtracted overall percentage cytokine expression above will be presented by planned time point separately for each T cell and stimulation antigen. The median overall cytokine response (%) per treatment group will be represented by a horizontal line. A dot plot will also be provided for DMSO (i.e., background) overall cytokine response (%) results.

In addition, the median background-subtracted overall cytokine response for the stimulation antigens (PSA, PAP, 5T4, STEAP1) will be displayed altogether in a stacked bar plot for PSA responders and for non-responders by planned time point.

The 15 background-subtracted cytokine combinations (%) (**Error! Reference source not found.**) and background-subtracted overall cytokine response (%) at Day 35 and Day 64 will be presented using polyfunctional profile plots separately for each T cell and stimulation antigen. Each of the cytokine combinations will be presented under the plot using Boolean values (+, -).

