| Immunogenicity assessments | | | | | | | | |
| Blood for PBMC assessment ^f | | | | | X | X | | |
| Blood for anti-antigen antibody assessment | | | | | X | X | | |

Abbreviations: AESIs- Adverse Events of Special Interest, d=days, EOT=End of Trial, PBMC=peripheral blood mononuclear cells, PSA=prostate-specific antigen, PSMA=prostate-specific membrane antigen

^a Participants will only have 1 EOT visit at either Months 6 or 24 or earlier in the event of initiation of new therapy (such as ADT) or development of unequivocal metastatic prostate cancer. Participants with no PSA response in the first 6 months will not enter the Long-Term Follow-up Period. Participants with a PSA response through Month 6 will enter the Long-term Follow-up Period.

^b Visits during the Follow-up Periods are from Day 1. Windows are relative to the target date of the visit.

^c If a cardiac event is reported, blood should be taken for an additional assessment of troponin T and the participant should undergo an additional ECG and echocardiogram at the earliest opportunity

^d If troponin T test result is abnormal, a re-test on the following day is required.

^e PSMA scan can be performed at any time for participants who had a positive PSMA scan prior to screening and where a 50% reduction from baseline in PSA is observed.

^fOnly required at sites qualified by Barinthus Biotherapeutics to perform PBMC isolation/processing.

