4.1.4 Duration of Trial for Participants

The trial consists of the following periods:

- Screening Period: Up to 42 days from informed consent until VTP-850 prime dose.
- Intervention Period: From VTP-850 prime dose until the Day 91 Clinic Visit.

Short-term Follow-up Period: All participants will be followed monthly from the end of the intervention period until the Month 6 Visit or until start of new therapy such as ADT or development of unequivocal metastatic prostate cancer, if sooner. If a participant does not have a PSA response by their Month 6 visit, they will complete their EoT visit and will not enter the Long-term Follow-up Period.

Long-term Follow-up Period: Participants who have PSA response will be followed for an additional 18 months, up to 24 months from first dose, or until start of new therapy such as ADT or development of unequivocal metastatic prostate cancer, if sooner. Clinic visits will be monthly to Month 12 and bimonthly thereafter. If a participant has a significant decrease in PSA but does not meet the criteria for a PSA responder e.g., the confirmatory measurement is not yet performed, discuss with the Medical Monitor whether the participant should continue follow-up.

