2.6. Exploratory Efficacy Variable(s)

2.6.1. Intracellular Cytokine Staining

Prostate cancer-specific CD4+ and CD8+ T cell subsets will be further defined by phenotypic markers of activation, differentiation, memory and functionality using multiparameter flow cytometry assays such as intracellular cytokine staining (ICS). Immunogenicity endpoints analyzed by Barinthus Bio's Immunology laboratory will be evaluated from PBMC samples at Days 1, 29, 36, 57, 64, 91 and Months 8 and 12. Participants who receive an optional third MVA dose or whose second MVA dose is delayed because of the study pause will have additional PBMC samples collected after this last MVA dose.

For the ICS data, the general class of endpoints is the background-subtracted (i.e., DMSO-subtracted) percentage of CD4+ or CD8+ T-cells that positively express at least one of four cytokines (as described in Table 2). For CD4+ cells, the four cytokines of interest are CD154, IFNg, TNFa, and IL-2. For CD8+, the four cytokines of interest are CD107a, IFNg, TNFa, and IL-2 (i.e., IFNg, TNFa, and IL-2 are common cytokines of interest for CD4+ and CD8+ cells).

Cytokine expression in CD4+ and CD8+ cells will be assessed for four stimulation antigens: PSA, PAP, 5T4, STEAP1. Hence, for each timepoint for a participant, the ICS data will include 4 records of interest, one for each of the 4 stimulation antigens¹.

Background-subtracted percentages of positive cytokine expression are calculated as follows:

1. For each sample's four stimulation antigens (i.e., PSA, PAP, 5T4, STEAP1), calculate the percentage of CD4+ or CD8+ cells with total positive cytokine expression (i.e. all combinations in Table 2) by dividing the cell count with positive expression by the respective total CD4+ or CD8+ count for the sample.
2. Likewise, calculate the background percentage of CD4+ or CD8+ cells with positive expression using the same method and the sample's DMSO record.
3. The background-subtracted percentage with positive cytokine expression is the subtraction of the background percentage expression calculated in Step 2 from the percentage calculated in Step 1. If the background expression is greater than the stimulation antigen's expression, the percentage with positive expression for the stimulation antigen should be set to 0.

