6.6.4.2. ELISpot response

These analyses will be presented using the Immunogenicity analysis set both overall and separately by whether participants had or did not have an observed PSA response.

Average background-subtracted antigen-specific IFNg ELISpot response (SFU/10⁶ PBMC) will be presented for each stimulation antigen (PSA, PAP, 5T4, STEAP1). Descriptive statistics including n, mean, standard deviation, median, minimum, maximum, and 95% CI for the median based on order statistics will be presented for absolute values, change from baseline, and fold change from baseline at all planned time points (Days 1, 29, 36, 57, 64, 91 and Months 8 and 12). Fold change for values i and j is defined as:

$$(\text{Value j}/\text{Value i})-1.$$

Where value j is the IFNg ELISpot response value at a non-baseline timepoint and value i is the cytokine expression value at day 1. When value i is 0 a small constant, λ , will be added to the calculation. $\lambda=0.5\times\min(\text{non-zero value for all participants at all time points})$. In this case fold change will be calculated as:

$$((\text{Value j} + \lambda)/(\text{Value i} + \lambda))-1.$$

To identify statistically significant differences between baseline and Days 35 and 64, a Wilcoxon signed-rank test using change from baseline will be performed for PSA responders and for non-responders for each stimulation antigen.

Like the graphical summaries described for the ICS analysis, for average background-subtracted antigen specific IFNg ELISpot response (SFU/10⁶ PBMC) a dot plot will be presented by planned time point separately for each stimulation antigen (PSA, PAP, 5T4, STEAP1).

A stacked bar chart will also be displayed for the median total (pooled over antigens) response (SFU/10⁶ PBMC) by planned time point for PSA responders and non-responders.

In addition, a line plot of mean \pm SD of the total (pooled over antigens) response (SFU/10⁶ PBMC) for each treatment will be displayed by planned time point.

A summary of the number and percentage of participants who meet the responder criteria (i.e., those with a background-subtracted average result greater than the positivity threshold) will be presented at all planned time points.

The average background-subtracted antigen-specific IFNg ELISpot responses (SFU/10⁶ PBMC) will be listed by stimulation antigen for each participant at each time point.

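### Overall immunogenicity summaries and the ELISpot line plot run on to Months 8 and 12, when almost only PSA responders are still sampled, so the population changes after Day 91

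*SAP*

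**What the plan says.** **Sampling.** In the follow-up schedule (Protocol 1.3, Table 2) the cell-sample row reads "Blood for PBMC assessment ^f | | | | | X | X". Against the column headings, the two marks fall at Month 8 and Month 12. Both lie in the Long-term Follow-up Period, and nothing is taken at Months 4, 5 or 6.

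**Who is still there.** Footnote a to that table states: "Participants with no PSA response in the first 6 months will not enter the Long-Term Follow-up Period". On entry to the same period, Protocol 4.1.4 agrees: "If a participant does not have a PSA response by their Month 6 visit, they will complete their EoT visit and will not enter". SAP 5.1.3 defines long-term follow-up in the same way. There is one exception. For a man with a significant PSA fall that does not meet the response criteria, for instance because it is not yet confirmed, Protocol 4.1.4 tells sites to "discuss with the Medical Monitor whether the participant should continue follow-up".

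**Analysis.** SAP 2.6.1 says the immunogenicity endpoints "will be evaluated from PBMC samples at Days 1, 29, 36, 57, 64, 91 and Months 8 and 12", without saying that the last two visits are essentially for responders only. SAP 2.5 does state that restriction for PSA. SAP 6.6.4.1 and 6.6.4.2 present results "both overall and separately by whether participants had or did not have an observed PSA response". Absolute values, change and fold change from baseline are all tabulated, and the stated span is "at all planned time points (Days 1, 29, 36, 57, 64, 91 and Months 8 and 12"). SAP 6.6.4.2 also plans a line plot of mean and SD total ELISpot response, which "for each treatment will be displayed by planned time point". The immunogenicity set (SAP 4.6) needs only a baseline and one later sample. Missing values are not imputed (SAP 2.6.1 and 2.6.2).

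**The concern.** Men without a PSA response belong to the immunogenicity set and contribute up to Day 91. They then drop out of the cell-sample schedule because of their PSA outcome, not at random. An overall mean or median at Month 8 is therefore taken over a different group of men from the one at Day 91, and the line plot connects the two.

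At stake is how durability is read. Protocol 4.1.3 expects stronger T-cell responses to go with better efficacy. If that is right, responders sit above non-responders, and an overall line that holds up or rises after Day 91 could come from selection alone. It could then be taken as lasting immunity for the regimen.

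**Working it through.** **Inputs**
- Visits, entry rule and displays: as set out above.
- Response rate p: the documents give no observed rate. Protocol 11.4 plans on 20%, so 20% is used as an assumption, with 10% and 30% as the range.
- Cohort size: 6 fully dosed men in each of Cohorts 2 and 3 (Protocol 4.1.1). Phase 1 total: about 25 (SAP 2.3).
- D, the responder minus non-responder mean: not given, so results are expressed in units of D.

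**Step 1: the plan's own figure.** Protocol 11.4 gives a 76.6% chance of 4 or more responders in 25 at a true rate of 20%. The exact binomial tail P(X ≥ 4 | 25, 0.20) is 0.7660, which agrees. The figure is not in dispute; it is the source of the 20%.

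**Step 2: shift from composition alone.** Let responders have mean R and non-responders mean N, both constant over time, with D = R - N.
- Up to Day 91: overall mean = pR + (1-p)N.
- Months 8 and 12: overall mean = R, if only responders are sampled.
- Difference: R - pR - (1-p)N = (1-p)(R - N) = (1-p)D.

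| p | Shift in overall mean |
|---|---|
| 10% | 0.9D |
| 20% | 0.8D |
| 30% | 0.7D |

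If D is zero there is no shift. If D is negative the shift goes down.

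**Step 3: illustration (levels assumed, no source in the documents).** With R = 300 and N = 100 SFU, both flat, and p = 20%, the overall mean is 0.2 × 300 + 0.8 × 100 = 140 up to Day 91 and 300 afterwards. That is an apparent 2.1-fold rise (300/140) with no true change. At 10% it is 300/120 = 2.5-fold, and at 30% it is 300/160 = 1.9-fold. With a smaller gap, R = 150 and N = 100 at 20%, the mean goes from 110 to 150, or 1.4-fold.

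**Step 4: how many men the late points rest on.** These figures assume that every responder gives a late sample. Sites not qualified to process cells, and exits for new therapy or metastasis, would lower them.

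| | p = 10% | p = 20% | p = 30% |
|---|---|---|---|
| Expected men sampled late, cohort of 6 | 0.6 | 1.2 | 1.8 |
| Chance of none, (1-p)^6 | 53% | 26% | 12% |
| Chance of 0 or 1 (no SD), (1-p)^6 + 6p(1-p)^5 | 89% | 66% | 42% |
| Expected men sampled late, of 25 | 2.5 | 5 | 7.5 |
| Chance of at least 6 of 25 | 3% | 38% | 81% |

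Six matters because the planned 95% CI for the median uses order statistics. The widest such interval covers 1 - 2 × 0.5^n: 93.75% at n = 5 and 96.9% at n = 6. With fewer than six late samples the interval cannot reach 95%.

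**The case against.** The strongest reply is that the SAP already does most of what is needed. Both sections split results by PSA response and report within-man change and fold change from baseline at every visit, so the responder-only change from baseline at Months 8 and 12 is already planned. n is tabulated at each time point, the dot plots show individuals, and the ELISpot values are listed by participant. All of this stands, and it limits the harm. It does not alter the overall tables. Change from baseline is within-man at each visit, but its overall mean still passes from all sampled men to responders between Day 91 and Month 8.

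The opening sentence of SAP 6.6.4.2 can also be read as applying the PSA split to the line plot. If so, the plot would be produced both ways, and the overall version would still join the two groups.

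A reader might go further and infer any of the following. The documents do not support them.
- *All the immunogenicity figures are misleading trends.* Only the ELISpot line plot is a joined series. The other figures are dot plots with a median line, stacked bars already split by PSA response, and profile plots at early visits.
- *Non-responder results at Months 8 and 12 must be empty.* Protocol 4.1.4 allows some men who do not meet the response criteria to be kept on after discussion. They would be few, and they too are selected on a PSA fall.
- *The late points will be presented without any warning.* Table and figure layouts sit in separate shells that are not available here and may carry n or a footnote.

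Finally, no planned decision rests on these displays. The Phase 2 regimen is chosen on safety data (Protocol 4.1.1), and Stage 2 opens on PSA responses and safety (Protocol 4.1.2). That is correct and sets the severity.

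**Conclusion.** The point holds as a minor one. Followed as written, SAP 6.6.4.1 and 6.6.4.2 carry overall summaries, and one line plot, across a change of population after Day 91. With no true change over time, the overall mean shifts by (1-p)D: 0.8D at a 20% response rate and 0.7D to 0.9D for 30% to 10%.

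This rests on three assumptions: the response rate, a non-zero D, and late samples coming essentially from responders. The size and sign of D are unknown. A reader might infer that the plan will overstate durable immunity. The documents support only that it could, if responders have the stronger T-cell responses. What is affected is the interpretation of an exploratory, descriptive endpoint. No error rate and no trial decision is touched.

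**What to change.** - End the summaries that are not split by PSA response, and the per-treatment ELISpot line plot, at Day 91.
- Show Months 8 and 12 only for the men still in long-term follow-up. Label them as such with n, and give change from the same men's baseline and Day 91 values.
- List individually any late samples from men who do not meet the PSA response criteria, so that those data are kept.
- Add to SAP 2.6.1 the same kind of restriction that SAP 2.5 already states for PSA.

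The cost is the loss of a pooled late time point, a short SAP amendment and minor changes to table and figure shells. No new data and no protocol change are needed.
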